During initial screening and recruitment, it will be necessary to acquire potential participants' names and medical record numbers. Medical record numbers will be used to confirm the patients' diagnosis and home TPN usage by reviewing electronic medical records. Names are necessary to obtain permission to approach the patients from the patients' physicians. This information will be stored electronically in a password-protected file on a computer in room M-421. After screening and recruitment, patient names will be replaced anonymous study I.D. numbers. For patients choosing not to participate in the study, medical record numbers will also be deleted, and standard of care will be continued.

Following consent, each subject will be asked to complete a "TPN Central Catheter Self-Care Questionnaire" (Appendix 1). The primary role of the enrollment questionnaire is to assess for baseline comfort level to manipulate a central catheter at home. In addition, following enrollment, electronic chart review will be performed to assess for clinical and laboratory variables within three months of enrollment (complete blood count, renal function, liver function studies, type of catheter placement, extent and duration of disease and comorbid conditions [Charlson score]).

All enrolled patients will receive baseline in-person hands-on training for catheter use. Then the patients will be randomly assigned to the control group (written instructions) or the intervention group (provided video link).

A baseline entry questionnaire will be administered to assess the patients' comfort level for central catheter use and indications for PN. Each subject will use their study I.D. in lieu of their name. Then patients in the intervention group will be given a link to the educational video, which they can access as many times as they prefer.

Six weeks following enrollment, study participants will be asked to complete a second "TPN Central Catheter Teaching and Self-Care Questionnaire" (Appendix 2) via an email or secure text link generated from patient.iq. to reassess participants' comfort level of catheter self-care.

Six months following enrollment, study participants will be asked to complete a "Conclusion of Study Questionnaire" (Appendix 3) via an email or secure text link generated from patient.iq. The role of the concluding questionnaire is to assess for subjective reports of their confidence and comfort level in central line self-care.

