There is a minor risk of loss of confidentiality with participation in this study since subject identifiers will be collected. However, all study data will be recorded in a database where names and medical record numbers will be removed and replaced with a study I.D. Only the study staff will have access to the key which links the study code to the subject's identity.

Patients may receive no direct benefit from participation in this study, but it is anticipated they will benefit from improve catheter self-care techniques, and an improved physicians' understanding of catheter associated bloodstream infections.

Special Precautions

No specimens will be collected during this study. Standard precautions will be provided during all patient encounters and clinical care.

Special precautions will be taken by research staff to ensure confidentiality. All data review will be performed electronically on a password-protected computer in a locked and limited access area.

Data will be coded in case the study team needs to go back and re-check data or look into abnormalities. Subjects are assigned a unique study code in place of their name and MRN. Only the study staff will be able to link data with subjects' identifiable information. Upon termination of the study, the coding link will be destroyed, leaving only completely de-identified data.

Experimental controls and use of placebos

N/A

Number of experimental subjects

One hundred (100) subjects will be included in the study.

Data Analysis

The rate of CRBSI will be determined. Risk factors for the CRBSI will be assessed in univariable and multivariable analysis based on pre-defined clinical and subjective risk factors.

Statistical justification

The rationale for the number of subjects is as follows. With 30% rate of bloodstream infection, and a 70% power and 95% confidence interval, the total sample size required would be 93 patients in order to see a reduction in the rate of bloodstream infection. Suppose a 10% rate for loss to follow-up, the total subjects will be 100 patients.

At the end of the study, the rate of CRBSI will be calculated and compared between the TPN video group and the control group using an unpaired Student's T test. The frequency of TPN video use will be reported as quantitative data based on discrete values. The comfort level of CVC handling will be aggregated, and the mean value will be compared between the video group and the control group using an unpaired Student's T test.

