Appendix 1: Central Catheter Teaching and Self-Care Initial Questionnaire

Name: _____ Subject ID: _____
 Date: _____ Email: _____

- 1) What type of central venous catheter do you have?
 PICC line Tunneled catheter (Hickman)
- 2) How many lumens (or "ports") on your catheter? _____
- 3) What are the cycle hours of your PN (parenteral nutrition)? _____ hours
- 4) Do you use any other IV medications through the catheter (excluding heparin lock, etc for catheter maintenance only)? Yes No

What IV medications?

	Yes	No
Do you currently have an ostomy?		
Do you currently have a fistula anywhere in your body?		
Do you currently have a G tube?		
Have you ever worked with IVs in a home or employment setting?		

- 5) How comfortable do you feel about taking care of your central venous catheter?
 - Very uncomfortable
 - Somewhat uncomfortable
 - Neutral
 - Somewhat comfortable
 - Very comfortable

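### The primary CRBSI comparison is unadjusted although catheter type is recorded at baseline; pre-specifying adjustment for it would be a cheap safeguard against chance imbalance

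*Combined protocol and SAP*

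**What the plan says.** The section Statistical justification gives the only between-arm analysis of infection. It states that "the rate of CRBSI will be calculated and compared between the TPN video group and the control group", and the test named is an unpaired t test. No covariate or stratum is named.

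Catheter type is collected twice. Item 1 of Appendix 1, completed at enrolment, asks "What type of central venous catheter do you have" and offers PICC or tunneled (Hickman). The chart review under Methodology covers "type of catheter placement, extent and duration of disease and comorbid conditions [Charlson score", among other variables, within three months of enrolment. Item 2 of Appendix 1 asks for the number of lumens.

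Methodology describes the allocation only as random. It gives no ratio and no stratification factor.

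Data Analysis separately plans univariable and multivariable modelling of risk factors for CRBSI. It does not list the factors, does not say whether the study arm is one of them, and does not link the model to the arm comparison.

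**The concern.** In a trial of this size, randomisation alone can leave the arms visibly different on a baseline factor. If that factor also predicts infection, the crude difference in the trial as run mixes the effect of the video with the effect of the imbalance. The data needed to deal with this are already being collected, but the plan does not use them in the primary comparison.

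The practical risk is one of timing. If an imbalance in catheter type appears once the data are in, any adjustment will be post hoc and open to challenge. A covariate named in advance avoids that.

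**Working it through.** **Inputs from the documents.** "With 30% rate of bloodstream infection, and a 70% power and 95% confidence interval"; "the total sample size required would be 93 patients"; 10% loss to follow-up; 100 enrolled.

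**Assumptions, because the documents are silent.** 1:1 allocation; a two-sided 5% test; the 30% is the control rate; CRBSI is counted as yes or no per patient; the video-arm rate is 10% to 15%; half the patients have a PICC. The risk ratio between catheter types is varied from 1 to 3.

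**1. The plan's own figure.** The target rate is missing: the aim is only "in order to see a reduction in the rate of bloodstream infection". At an assumed 10% in the video arm, the unpooled formula gives

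N = 2 × (1.960 + 0.524)² × (0.30 × 0.70 + 0.10 × 0.90) / 0.20² = 92.6, or 93.

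So 30% against 10% is a plausible reading of the design, but not a stated one.

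**2. Patients and events analysed.** 100 × 0.90 = 90, or 45 per arm. Expected events are 45 × 0.30 + 45 × 0.10 = 18, or 45 × 0.30 + 45 × 0.15 = 20.

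**3. Chance imbalance.** With K of the 90 patients on a PICC, the number falling in one arm of 45 is hypergeometric. Summing over splits whose between-arm gap reaches the threshold gives:

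| Patients with the factor | 10 points or more | 15 points or more | 20 points or more |
|---|---|---|---|
| 45 of 90 (50%) | 40% | 21% | 9% |
| 27 of 90 (30%) | 36% | 17% | 6% |

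These probabilities move in steps. With 45 of 90 the gap can only be an odd multiple of 1/45, so the first value above 15 points is 7/45 = 15.6 and 20 points is exactly 9/45. With 44 or 46 of 90 the same sum gives 14% and 6%. The normal approximation, with SD √(2 × 0.25/45) = 10.5 points, gives 15% and 6%. The 21% is therefore the upper end of roughly 14% to 21%.

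**4. Effect on the estimate.** Shift = imbalance × risk gap. With an assumed 20-point gap in both arms, 0.20 × 0.20 = 4 points. If the video shrinks the gap in its own arm in proportion (20 to 6.7 points at 30% against 10%), the shift is 0.10 × 20 + 0.10 × 6.7 = 2.7 points.

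The standard error of the crude difference is √[(0.21 + 0.09)/45] = 8.2 points at 30% against 10%, or √[(0.21 + 0.1275)/45] = 8.7 at 30% against 15%. A 4-point shift is thus a little under half a standard error.

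**5. Precision.** Simulated crude and Mantel-Haenszel risk differences (45 per arm, 50% prevalence, control rate averaging 30%, 400,000 trials per setting):

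| Assumed risk ratio between types | Control risks | Variance change, 30% vs 10% | Variance change, 30% vs 15% |
|---|---|---|---|
| 1 | 30% / 30% | 1% more | 1% more |
| 1.5 | 36% / 24% | about none | about none |
| 2 | 40% / 20% | 2% less | 2% less |
| 3 | 45% / 15% | 6% less | 6% less |

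Both estimators average to the true difference in every row. A 6% fall in variance cuts the standard error by 3% (√0.94 = 0.97), which takes the 95% half-width from 1.96 × 8.2 = 16.0 points to about 15.5.

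Adding a second binary factor such as lumen number, in a linear model at 30% against 10%, gave from 2% more variance (neither factor prognostic) to 7% less (risk ratios of 3 and 2).

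**The case against.** The strongest reply is that the premise is not in the documents. Nothing in them says that catheter type or lumen number predicts CRBSI. The independent risk factor named in the Background is parenteral caloric intake. If type is not prognostic, nothing is lost by ignoring it, and adjustment costs about 1% in variance. This stands, and it is why every shift and precision figure above is conditional.

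Three stronger readings are tempting, and the documents do not support them.

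- A reader might infer that the crude comparison is biased or invalid. It is not. Randomisation makes it valid on average, and chance imbalance is already part of the sampling error that its confidence interval reflects. The point concerns the one trial that will be run.
- A reader might infer that the plan is certain to give up precision. The gain runs from slightly negative to modest, so chance imbalance is the better argument.
- A reader might infer that the multivariable analysis leaves out the video effect. The plan does not say so. It only fails to say that the arm is in the model or that the model bears on the primary comparison.

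It is also fair to object that large imbalances are not the usual case. The average absolute gap at 50% prevalence is about 8.5 points, which with a 20-point risk gap shifts the estimate by only 0.085 × 20 = 1.7 points.

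**Conclusion.** The point holds as a recommendation. The primary comparison is unadjusted, catheter type is available at baseline, and neither the stated randomisation nor the risk-factor analysis fills the gap. With about 45 per arm, an imbalance of 15 points or more has about a 21% chance at 50% prevalence (nearer 14% at adjacent counts), and 20 points or more about 9%. Such an imbalance would shift the estimate by up to about 4 points under an assumed 20-point risk gap, and not at all if type is not prognostic. The precision gain is uncertain and at best small.

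The size rests on 1:1 allocation, 90 analysed patients, the assumed prevalence and the assumed prognostic strength. Only the 90 follows from the plan's own figures.

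**What to change.** In Statistical justification, name as the primary estimate a Mantel-Haenszel risk difference with 95% confidence interval, stratified by catheter type (PICC or other). Report the crude risk difference as a sensitivity analysis.

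Define the stratum by the catheter in place before randomisation. Take it from Appendix 1 and check it against a chart entry dated before randomisation. The check helps because Appendix 1 offers only two types. The date matters because a three-month window around enrolment could pick up a catheter placed after randomisation.

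Lumen number (1 against 2 or more) may be added but is optional, since only about 18 to 20 events are expected. Whatever is chosen should be fixed before outcomes are reviewed. The plan should also say whether the arm enters the multivariable risk-factor model.

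The cost is a sentence or two of text and no new data item. The statistical downside is about 1% more variance if catheter type does not predict CRBSI.

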Fortunately, there are interventions that reduce risk for bloodstream infection in home TPN. In a retrospective study, chlorhexidine gluconate transparent antimicrobial dressing reduced CRBSI from eight cases to zero case in 12 months.¹⁵ Another research study found that patients with parenteral nutrition who are managed by a dedicated nutrition support team are less likely to develop CRBSI at 24 months than a variety of physicians (1.3% vs 26.2%).¹ More importantly, patient engagement and education program has been proven feasible and potentially effective. An oncology unit in Denmark developed an education program for 42 out of 82 randomized patients with tunneled central vein catheters. 88% of the 42 patients completed the training, and the 42 patients had 50% less CRBSI in a five-month period.¹⁶ A group in MD Anderson Cancer Center designed an in-person and video education program for central catheter care. After 1 year, 95% of the participating patients caring for the catheters at home, and 97% of them reported confidence and satisfaction in catheter care.¹⁷

We developed an education video addressing the aseptic techniques to safely handle central catheters at home for TPN use. It will be hosted in a mobile app with a secure link. Our primary aim is to assess the effect of the video training supplementation prior to discharge on the rate of CRBSI over a 12-month period of time. Our secondary aims are

to assess the patient's comfort level when handling catheters for patients newly initiated home TPN.

Hypothesis

We hypothesize that 1) the video will improve rates of CRBSI compared to a control group receiving written catheter instructions; 2) the video will improve patients' comfort level with handling central catheters; 3) patients will find the video easy to use.

Participants

Inpatient adult patients who are discharged home for the first time on home TPN will be approached for consent and inclusion in this prospective study design.

Study duration

24 months

Methodology

Inclusion Criteria

1. Patient will be discharged to start TPN at home.
2. Age ≥ 18 yrs.
3. Ability to understand and sign written consent form.
4. English-speaking patients.
5. Patients who are willing to self-administer TPN at home.

Exclusion Criteria

1. Patients without consent
2. Patients who have been on home TPN prior to the index admission at any time in the past
3. Non-English-speaking patients
4. Patients who will not self-administer TPN.

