If a subject fails to respond to these electronic questionnaires, the IRB-approved study staff will approach he/she during a standard GI Nutrition follow-up clinic visit to obtain answers for the questionnaire via a secure link on a tablet device.

The follow-up period will not exceed one year beyond the inclusion date. At the end of one year, the IRB-approved study staff will gather clinical information from the electronic medical record to determine if each subject has had a CRBSI event. Per CDC, CRBSI is defined as a laboratory confirmed infection where a Central Venous Catheter (CVC) is in place for over 2 calendar days prior to a positive culture and is also in place the day of or day prior to culture. And not deemed as a result from contamination by the primary hospital team at the time of the treatment.

The subjects will undergo weekly laboratory tests (complete blood count, electrolytes, liver function, and kidney function) as part of their routine standard of care to ensure the TPN formula is up to date and meets subjects' nutritional and metabolic needs. If a subject seeks care outside of UChicago, subject's UChicago care team members will obtain permission to have the health information released to UChicago, as part of the subject's standard of care. If patient wishes to transfer care of their TPN and CVC permanently to another institution, then their participation in this study will be terminated.

Additionally, subjects will be followed-up weekly via phone by their care team at UChicago as part of subjects' routine standard of care to ensure safe use of CVC and TPN infusions.

Study Schema

Assessment/Procedure	Visit 1	Visit 2	Visit 3	Visit 4
Informed consent	X			
Data collection: Demography and medical history	X			
Randomization	X			

Watch video/ follow written instructions	X	X	X	
Complete questionnaire	X	X	X	
Review medical, surgical, and hospitalization records for CRBI evaluation				X

Location

Patients will be consented at the University of Chicago's Center for Care and Discovery and Mitchell Hospital. All obtained data will be stored in a password protected computer or a locked drawer in the research office in M-421.

Potential risks and benefits

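### The yes/no CRBSI outcome is compared with a t test for means, and no effect measure with a suitable interval is named

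*Combined protocol and SAP*

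**What the plan says.** The primary aim in Background is the effect of the video "on the rate of CRBSI over a 12-month period of time". In Methodology, staff review each record at one year "to determine if each subject has had a CRBSI event", so each patient contributes a yes or a no. No count per patient and no rate per catheter-day is defined.

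Statistical justification sizes the trial on a proportion: "With 30% rate of bloodstream infection, and a 70% power and 95% confidence interval". It gives 93 patients, raised to 100 for 10% loss. It does not give the video-arm rate the trial hopes to detect.

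The only arm comparison named for this outcome is that "the rate of CRBSI will be calculated and compared between the TPN video group and the control group using an unpaired Student's T test". The same test is named for the mean comfort score. Data Analysis adds risk-factor models but no measure of the difference between arms. The only confidence interval mentioned is the one in the sample-size sentence. Methodology says that patients are randomised but gives no allocation ratio.

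**The concern.** Student's t test compares means and assumes one common variance. For a proportion the variance is p(1-p), so a real effect makes the two variances differ. The t test's standard error is then right only when the arms are the same size. If the lower-risk arm is the larger one, the interval is too short; if it is the smaller one, the interval is too long. With few events, a symmetric interval fits poorly even with equal arms. A reader of the results will want the size of the reduction and its uncertainty, and the plan leaves that to whatever interval accompanies the t test.

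**Working it through.** **Inputs.** From Statistical justification: 30% (taken as the control rate, since the arm is not named), 70% power, 95% confidence (read as two-sided alpha 0.05), 93 patients, 100 enrolled, 10% loss. Evaluable: 100 × 0.90 = 90. Assumed: the video-arm rate and the arm sizes.

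**The plan's 93.** The stated inputs do not fix it without a video-arm rate. The pooled two-proportion formula with 9.6% reproduces it:

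- mean rate = (0.30 + 0.096)/2 = 0.198
- n per arm = [1.960 × √(2 × 0.198 × 0.802) + 0.524 × √(0.21 + 0.0868)]² / 0.204² = (1.105 + 0.286)² / 0.0416 = 46.4
- total = 92.9, or 93

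This match is not unique. The unpooled formula with 10% gives 2 × 6.172 × (0.21 + 0.09)/0.04 = 92.6. I use 9.6% and vary it below.

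**Why the interval goes wrong.** The true variance of the difference is v₁/n₁ + v₂/n₂, with v₁ = 0.30 × 0.70 = 0.21 (control) and v₂ = 0.096 × 0.904 = 0.0868 (video). The pooled form is very nearly v₁/n₂ + v₂/n₁, which attaches each variance to the wrong arm size.

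- 40 control/50 video: true SE = √(0.00525 + 0.00174) = 8.4 points; pooled SE ≈ √(0.00420 + 0.00217) = 8.0 points.
- 36/54: true SE = √(0.00583 + 0.00161) = 8.6 points; pooled SE ≈ √(0.00389 + 0.00241) = 7.9 points.
- 45/45: the two are equal.

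**Coverage of nominal 95% intervals.** For every possible pair of event counts I computed the pooled-t and Newcombe intervals, then summed the binomial probabilities of the pairs whose interval contains the true difference (90 patients).

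| Rates, control v video | Arms, control/video | Pooled t | Newcombe |
|---|---|---|---|
| 30% v 9.6% | 45/45 | 95.2% | 95.3% |
| 30% v 9.6% | 40/50 | 92.9% | 95.4% |
| 30% v 9.6% | 36/54 | 92.0% | 94.7% |
| 30% v 9.6% | 50/40 | 96.2% | 95.0% |
| 30% v 9.6% | 54/36 | 96.9% | 95.8% |
| 10% v 2% | 45/45 | 92.6% | 97.4% |

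**Range over the unstated video rate.** At 40/50, t coverage is 93.5% for 30% v 10%, 93.9% for 30% v 15% and 94.3% for 30% v 20%. The smaller the true effect, the smaller the fault.

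**How likely is imbalance?** Under simple 1:1 allocation (an assumption), the video arm has 50 or more of 90 with probability P(Bin(90, 0.5) ≥ 50) = 17%, and 54 or more with probability 3.6%.

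**The test itself.** Power at 30% v 9.6%, 45/45, is 70.8% (t) and 70.7% (N-1 chi-square). The two tests decide differently in 8 of 2,116 possible tables at 45/45, in 2 of 2,091 at 40/50 and in none at 36/54. Maximum t-test type I error over common rates of 0.5-40% is 6.0% at 45/45 (near a rate of 8.5%), 5.3% at 40/50 and 5.2% at 36/54. At a common rate of 30% it is 4.8-5.1% for these splits.

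**The case against.** The strongest defence is that the t test on 0/1 data is nearly the same test as the chi-square at these sample sizes. That stands, and it limits the point.

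A reader might infer that unequal arms distort the error rate. They do not in themselves: if the video has no effect, both arms share one risk and one variance, and pooling is correct. The 6.0% maximum arises with exactly equal arms and far from the planned 30%.

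A reader might also cite a sparse result such as 4 v 0 of 45, where t gives p = 0.041 and Fisher p = 0.117. The N-1 chi-square gives p = 0.042, so this is no argument for the chi-square over t. What it does show is the interval: 0.4 to 17.4 points with t, -0.6 to 20.7 with Newcombe.

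Nor do the documents support planning for very rare events in both arms. The 1.3% in Background is a 24-month figure for patients managed by a nutrition support team, not for a video over 12 months.

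Two further defences stand in part. The plan promises no interval for the arm difference and no unequal allocation, so the coverage loss is conditional; 36/54 would be uncommon under simple 1:1 allocation. And the word rate could mean events per catheter-day, which would need another analysis, but the record review in Methodology points to yes/no.

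**Conclusion.** The point holds as a mismatch between outcome and method, and its weight lies in the interval. The plan names a test for means for a yes/no primary outcome and no effect measure with an interval. Using the t interval would cost about 2 to 3 points of coverage if the video arm is moderately larger and the effect is as large as the sample size implies. It would cost about 2.4 points (95.0 - 92.6) with equal arms at 10% v 2%. With near-equal arms at the planned rates it costs almost nothing, and the significance decision barely changes. These sizes rest on 90 evaluable patients and on assumed video-arm rates and arm splits. This is a cheap correction that should be made; it does not invalidate the trial.

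**What to change.** Replace the sentence on the primary comparison in Statistical justification with:

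> The proportion of patients with at least one CRBSI will be compared between the randomised groups as a difference in proportions with a 95% Newcombe interval; the primary p-value is from the N-1 chi-square test, and if any expected count is below 5, Fisher's exact p-value governs instead.

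Keep the t test for the comfort score only.

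**Cost.** One sentence, with no new data or patients. At 30% v 9.6% and 45/45 about 45 × 0.30 + 45 × 0.096 = 17.8 events are expected, so the smallest expected count is about 8.9 and the chi-square will nearly always apply. Fisher should not lead throughout: at 30% v 10% with 50 per arm it would cut power from 0.72 to 0.64.

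The downside falls on sparse results. At 10% v 2% only 4.5 + 0.9 = 5.4 events are expected, so Fisher, which is conservative, would usually govern. The mean interval width there is about 23 points instead of 19, and such a result will look less favourable. The p-value and the interval can also disagree: the N-1 p-value and the Newcombe interval do so in 2.3% of trials at 30% v 9.6% and in 8.7% at 10% v 2% (45/45). That is why the governing p-value must be named in advance.

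### Baseline comfort is collected but not used: the secondary aim rests on an unadjusted t-test of an undefined aggregated mean, with no visit named

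*Combined protocol and SAP*

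**What the plan says.** Background gives as the secondary aim the assessment of "comfort level when handling catheters for patients newly initiated home TPN", and Hypothesis expects the video to improve comfort.

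Methodology has comfort measured three times:

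- **Enrollment (Appendix 1).** "The primary role of the enrollment questionnaire is to assess for baseline comfort level to manipulate a central catheter at home".
- **6 weeks (Appendix 2).** "Six weeks following enrollment, study participants will be asked to complete a second" form.
- **6 months (Appendix 3).** "Six months following enrollment, study participants will be asked to complete a" concluding form.

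Each form carries one comfort item with five ordered levels. The enrollment item asks about taking care of the catheter; the two follow-up items ask about using it.

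The only planned comfort analysis is in Statistical justification: "The comfort level of CVC handling will be aggregated, and the mean value will be compared between the video group and the control group", with an unpaired Student's t-test. The multivariable analysis under Data Analysis concerns risk factors for CRBSI, not comfort.

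Methodology mentions the baseline form twice. It appears first directly after consent. It appears again after the sentences on hands-on training and random assignment ("A baseline entry questionnaire will be administered to assess" comfort and the indications for PN), just before the video link is given. In the Study Schema, the row "Complete questionnaire" and the randomization row are both marked at Visit 1, with no order between them.

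**The concern.** Two things are at stake.

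First, precision. The protocol collects a baseline measure of the outcome and calls that the form's main purpose, then compares the arms without it. The aim rests on one five-level item in about 45 patients per arm, so precision is scarce. Adjusting for baseline multiplies the variance of the arm difference by about 1 − r², where r is the baseline-to-follow-up correlation, and uses data already in hand.

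Second, the outcome is not fixed. *Aggregated* may mean only that patients are pooled into a group mean, which is how Confidentiality uses a similar phrase. It may also mean that visits are averaged. On the first reading the visit is still unnamed. Either way, the result could be the 6-week score, the 6-month score or their mean, chosen after the data are seen.

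A related gap is that a baseline score is a clean covariate only if it is recorded before assignment is known, and the documents do not state that order. The two descriptions may well be one form described twice.

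**Working it through.** The plan has no comfort sample size, power or SD to reproduce. Its only sample-size statement is for CRBSI.

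**From the documents.** 100 patients are enrolled and 10% loss to follow-up is allowed for, so 100 × 0.9 = 90 are evaluable.

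**Assumed, because the documents are silent.** 1:1 allocation (45 per arm); the 10% loss rate, given for CRBSI, also applies to the questionnaires; a 0.5 SD effect; two-sided α = 0.05; r from 0 to 0.6.

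**Single follow-up visit, n per arm.**

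Power = Φ(0.5 / √(2(1 − r²)/n) − 1.96); 95% CI half-width = 1.96 × √(2(1 − r²)/n).

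- Unadjusted, n = 45: √(2/45) = 0.211; 0.5/0.211 = 2.37; Φ(2.37 − 1.96) = 0.660.
- Adjusted, r = 0.5: √(2 × 0.75/45) = 0.183; 0.5/0.183 = 2.74; Φ(2.74 − 1.96) = 0.782.

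| r | Power, 45 per arm | CI half-width (SD), 45 per arm | Power, 35 per arm |
|---|---|---|---|
| 0 (same as unadjusted) | 66.0% | 0.413 | 55.2% |
| 0.2 | 67.7% | 0.405 | 56.9% |
| 0.3 | 70.1% | 0.394 | 59.2% |
| 0.5 | 78.2% | 0.358 | 67.6% |
| 0.6 | 84.2% | 0.331 | 74.4% |

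The 35-per-arm column shows sensitivity to poorer questionnaire response. With other effects at 45 per arm and r = 0.5, power goes from 47.5% to 59.1% for 0.4 SD and from 81.2% to 90.8% for 0.6 SD. An unadjusted test would need 90/(1 − 0.25) = 120 patients to match the adjusted one at r = 0.5.

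**Mean of the two follow-ups**, with an assumed correlation of 0.5 between them. The variance is (1 + 0.5)/2 = 0.75, so unadjusted power is 78.2%. Adjusted variance is 0.75 − r², giving 80.4%, 83.1% and 91.8% at r = 0.2, 0.3 and 0.5.

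**Five-level item.** The formulas treat the score as continuous. In simulation (4,000 trials per setting; latent normal score cut at −1.5, −0.8, −0.2 and 0.6; 0.5 SD latent shift; 45 per arm), the t-test has about 57% to 58% power. ANCOVA has 57%, 59%, 61%, 66% and 72% at latent r = 0, 0.2, 0.3, 0.5 and 0.6. Type I error is 5.1% to 5.3% for both. Cutting the score into five levels weakens the correlation: latent 0.2, 0.3, 0.5 and 0.6 become about 0.18, 0.27, 0.45 and 0.55 on the item itself.

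**Open choice of outcome.** Under no effect, let Z₁ and Z₂ be the test statistics at 6 weeks and 6 months with correlation c, and Z₃ = (Z₁ + Z₂)/√(2 + 2c) that for their mean. The probability that at least one exceeds 1.96 in absolute value is 10.5%, 9.7% and 8.6% for c = 0.3, 0.5 and 0.7, against a nominal 5%.

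**If the enrollment score were averaged in.** Nothing in the text says it would be. On that reading the effect falls to 0.5 × 2/3 = 0.333 SD and the variance is (3 + 2(0.5 + 2r))/9. Power is then 58%, 55% and 49% at r = 0.2, 0.3 and 0.5, against 78% for the unadjusted mean of the two follow-ups.

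**The case against.** The planned test is valid: under randomization it is unbiased, and since the documents claim no power for comfort, no stated figure is wrong. That stands. The point concerns efficiency and an unfixed outcome, not bias.

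The gain depends on r, which may be low. Patients with any earlier home TPN are excluded, so enrollment comfort is rated before home experience; hands-on training may come between the scores; the item wording differs; and follow-up is 6 weeks to 6 months later. This is fair. At r = 0.2 to 0.3 the five-level simulation shows a gain of only 1 to 3 percentage points. But the cost of adjusting is one degree of freedom, so little is lost if r turns out low.

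If *aggregated* means averaging the two follow-ups, the unadjusted test already reaches 78%, as much as a single-visit ANCOVA at r = 0.5. True, but the plan does not say so, and adjustment adds to that reading as well.

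Six months may be the intended visit: the Appendix 3 form is called the concluding one, and the analysis paragraph opens by referring to the end of the study. That is plausible, but the phrase belongs to the CRBSI sentence and does not select a comfort visit. Likewise, the 9.7% describes what the wording permits, not anything the documents plan.

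The 35-per-arm case is only illustrative: the protocol lets staff collect missing questionnaires on a tablet at clinic visits, which should limit non-response.

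**Conclusion.** The concern holds. Baseline comfort is collected, the sole comfort comparison ignores it, *aggregated* is undefined and no visit is named.

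The undefined outcome needs no assumption to establish; its potential cost is a false-positive rate of roughly 9% to 10% if the best of three summaries were reported. The precision loss exists for any non-zero r, but its size cannot be taken from the documents. On a continuous scale with 0.5 SD and 45 per arm, power rises from 66% to between 68% and 84% for r of 0.2 to 0.6. On the simulated five-level item it rises from about 58% to between 59% and 72%. The effect, allocation ratio, response rate, correlations and cut-points are all assumed.

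This is a secondary aim and the planned test is not biased, so the change should be made but does not undermine the trial.

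**What to change.** 1. Define *aggregated* and name one primary comfort outcome: 6 weeks, 6 months or the mean of the two. Keep the enrollment score out of any average.
2. Replace the t-test with ANCOVA of that outcome on arm and baseline score. Alternatively, use one repeated-measures model of the 6-week and 6-month scores with arm, time, arm-by-time and baseline, and state in advance which contrast is primary, matching the outcome in item 1.
3. Report the adjusted mean difference with its 95% CI and the number responding per arm at each visit.
4. Because the item has five ordered levels, add a proportional-odds model with the same covariates as a sensitivity analysis.
5. Define baseline as the Appendix 1 answer completed before random assignment, and reconcile the two descriptions in Methodology accordingly.

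The cost is analysis-plan wording, one sentence on the order of questionnaire and randomization, and one degree of freedom for the covariate. No new data, visits or questionnaire changes are needed; the item wording can stay as it is for this comparison. If r proves low, the gain will be small.
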